3.2. General Methods

All data listings that contain an evaluation date will contain a relative study day. Pre-treatment and on-treatment study days are numbered relative to the day of study medication dosing, which is designated as Day 0. For example, the day prior to study medication will be Day -1 and the day after study medication will be Day 1.

All output will be incorporated into Microsoft Word or Excel files, or Adobe Acrobat PDF files, sorted and labeled according to the International Conference on Harmonisation (ICH) recommendations, and formatted to the appropriate page size(s).

Tabulations will be produced for appropriate demographic, baseline, efficacy, and safety parameters. For categorical variables, summary tabulations of the number and percentage of subjects within each category (with a category for missing data) of the parameter will be presented. For continuous variables, the number of subjects, mean, median, standard deviation (SD), minimum, and maximum values will be presented.

All data will be presented in by-subject data listings.

As this is a Phase 2 dose-escalation trial, formal statistical hypothesis testing will not be performed. Although exploratory confidence intervals (CIs) will be presented as described below, no formal statistical conclusions will be made based on these estimates.

Subjects will be analyzed in the cohort to which they were originally assigned. Data will be tabulated for each dose group (i.e., dose level, regimen, and pre-medication regimen).

Laboratory data collected and recorded as below the limit of detection will be set equal to the lower limit of detection for the calculation of summary statistics.

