### 9.2.1 Populations to be Analyzed

The following patient populations (i.e., analysis sets) may be evaluated and used for presentation of the data:

- Intent-to-Treat (ITT) Analysis Set: All patients who were enrolled and received study treatment. The ITT analysis set will be the primary set for the analysis of safety data.
- Per-Protocol (PP) Analysis Set: All patients in the ITT Analysis Set who had no major protocol violations.
- Pharmacokinetic (PK) Analysis Set: All patients in the ITT Analysis Set who have adequate data to determine a full PK profile.

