1.1.2. Study Objectives

The primary objective of this study is to evaluate the safety and tolerability of multiple doses of ALN-TTR02.

The secondary objectives of this study are:

- To characterize the plasma and urine pharmacokinetics (PK) of ALN-TTR02.
- To assess preliminary evidence of the pharmacodynamic (PD) effect of ALN-TTR02 on serum total TTR levels.

This statistical analysis plan (SAP) is designed to outline the methods to be used in the analysis of study data in order to answer the study objective(s). Populations for analysis, data handling rules, statistical methods, and formats for data presentation are provided. The statistical

analyses and summary tabulations described in this SAP will provide the basis for the results sections of the clinical study report (CSR) for this trial. Pharmacokinetic (PK) and pharmacokinetic/pharmacodynamics (PK/PD) analyses will be described in a separate analytical plan, will be performed by Alnylam Pharmaceuticals or its designated Contract Research Organization (CRO), and presented in a separate report (to be included in the CSR).

This SAP will also outline any differences in the currently planned analytical objectives relative to those planned in the study protocol.

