2. SUBJECT POPULATION

2.1. Population Definitions

The following patient populations (i.e., analysis sets) may be evaluated and used for presentation of the data:

- Intent-to-Treat (ITT) Analysis Set: All patients who were enrolled and received study treatment.
- Per-Protocol (PP) Analysis Set: All patients in the ITT analysis set who had no major protocol violations.
- Pharmacokinetic (PK) Analysis Set: All patients in the ITT analysis set who have adequate data to determine a full PK profile.

The ITT analysis set is the primary population for the analysis of PD and safety parameters. A secondary analysis of PD parameters will be performed for the PP analysis set. The PK analysis set is the primary population for the analysis of PK parameters.

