4.5. Safety Analyses

Safety analyses will be conducted using the ITT analysis set.

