4.5.2. Adverse Events

Adverse events will be displayed in tables and data listings using MedDRA system organ class (SOC) and preferred term.

Analyses of AEs will be performed for those events that are considered treatment-emergent, where treatment-emergent is defined per protocol as any AE with onset during or after the administration of study medication through 28 days after dosing, or any event that was present pre-infusion but worsened in intensity or was subsequently considered drug-related by the Investigator.

When determining whether an AE is treatment-emergent, partial dates will be handled as follows. If the day of the month is missing, the onset day will be set to the first day of the month unless it is the same month and year as study treatment. In this case, in order to conservatively report the event as treatment-emergent, the onset date will be assumed to be the date of treatment. If the onset day and month are both missing, the day and month will be assumed to be January 1, unless the event occurred in the same year as the study treatment. In this case, the event onset will be imputed as the day of treatment, in order to report the event conservatively as treatment-emergent. A missing onset date will be imputed as the day of treatment. If the resulting imputed onset date is later than a non-missing date of resolution, then the imputed onset date will be set to the resolution date. The imputed data is used solely for the purpose of determining whether an AE is treatment-emergent; actual dates as recorded on the eCRF will be presented in subject listings.

Adverse events are summarized by subject incidence rates; therefore, in any tabulation, a subject contributes only once to the count for a given SOC or preferred term.

The numbers and percentages of subjects with any treatment-emergent adverse event (TEAE), with any TEAE assessed by the Investigator as related to treatment (definitely or possibly related), with any TEAE that is severe in intensity, with any serious TEAE, with any TEAE leading to discontinuation of study medication, or with any TEAE considered a DLT will be summarized by dose group and overall.

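### SAP 3.2 tabulates safety and PD by the cohort assigned, so if a patient received another dose level, any toxicity would be counted under the wrong dose

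*SAP*

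**What the plan says.** SAP 3.2 gives one general grouping rule: "Subjects will be analyzed in the cohort to which they were originally assigned". The next sentence defines a dose group by dose level, regimen and premedication regimen. No later section exempts the safety or PD tables.

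On who is counted, SAP 4.5 says that "Safety analyses will be conducted using the ITT analysis set", SAP 2.1 says that "The ITT analysis set is the primary population for the analysis of PD and safety parameters", and Protocol 9.2.1 says that "The ITT analysis set will be the primary set for the analysis of safety data". The set itself is defined in SAP 2.1 as "Intent-to-Treat (ITT) Analysis Set: All patients who were enrolled and received study treatment". Neither document defines a separate safety or as-treated set, and neither has a rule on the dose received.

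On what the tables are for, SAP 1.1.2 says: "The primary objective of this study is to evaluate the safety and tolerability of multiple doses of ALN-TTR02". Under SAP 4.5.2 the counts of patients with treatment-emergent events, down to those "with any TEAE considered a DLT will be summarized by dose group and overall", are shown by dose group. Protocol 9.2 calls for tables by dose level without saying whether that means assigned or received. SAP 5 declares no change from the protocol.

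**The concern.** Analysis by assignment has a purpose in a randomised trial, where it preserves the comparison that randomisation created. Here SAP 1.2.2 marks randomisation as not applicable, and under Protocol 4.4.1 an eligible patient joins whichever cohort is open. There is no randomised comparison to preserve.

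The by-dose tables are meant to show what happened to patients after each dose. A patient who was assigned one level and received another would have any adverse event, dose-limiting toxicity (DLT) or TTR response reported under a dose that did not precede it. With 3 patients per planned cohort, one such patient alters two columns visibly. By-dose results also matter beyond this report, because Protocol 6.6 derives the recommended Phase 3 dose and regimen for the extension study from this trial.

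**Working it through.** **Group sizes.** SAP 3.1 plans 3 patients at each of 4 dose levels and up to 5 further cohorts of 3. The total is 4 × 3 + 5 × 3 = 27, which reproduces the stated maximum. SAP 3.5 pools cohorts dosed at the same level and regimen, so a group may hold 3 patients, 6, or at the extreme 3 + 5 × 3 = 18.

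**Illustration (assumed data).** One patient assigned to dose A receives dose B, another studied level, and has the only event. Let n_A and n_B be the group sizes by assignment.

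- By assigned cohort: A = 1/n_A and B = 0/n_B.
- By dose received: A = 0/(n_A − 1) and B = 1/(n_B + 1).
- The shift is therefore 1/n_A in group A and 1/(n_B + 1) in group B.

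Results, with exact (Clopper-Pearson) 95% intervals in percent:

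| n_A, n_B | Assigned: A | Assigned: B | Received: A | Received: B |
|---|---|---|---|---|
| 3, 3 | 1/3 = 33.3% (0.8–90.6) | 0/3 (0–70.8) | 0/2 (0–84.2) | 1/4 = 25.0% (0.6–80.6) |
| 6, 6 | 1/6 = 16.7% (0.4–64.1) | 0/6 (0–45.9) | 0/5 (0–52.2) | 1/7 = 14.3% (0.4–57.9) |
| 18, 3 | 1/18 = 5.6% (0.1–27.3) | 0/3 (0–70.8) | 0/17 (0–19.5) | 1/4 = 25.0% (0.6–80.6) |
| 3, 18 | 1/3 = 33.3% (0.8–90.6) | 0/18 (0–18.5) | 0/2 (0–84.2) | 1/19 = 5.3% (0.1–26.0) |

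In the planned 3-patient cohorts the shift is 33.3 points in A and 25.0 points in B, and the apparent ordering of the two doses reverses. Pooling reduces the shift only in the group that is pooled: in the third row B still moves by 25.0 points. The intervals are wide and overlap throughout, so what changes is which dose carries the event, not any inference.

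**PD.** The same misplacement enters the group means and nadirs of SAP 4.3.1. In a group of 3 the misplaced patient has weight 1/3 in the mean.

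**Where the dose actually given would appear.** SAP 4.5.1 summarises the amount received and lists drug administration, SAP 2.2 lists protocol violations, and SAP 4.5.2 lists adverse events and DLTs by patient. None of these regroups the by-dose tables. The per-protocol set can drop a major violator but moves nobody, and SAP 2.1 uses it only for a secondary PD analysis.

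**The case against.** The case for leaving the sentence alone has several parts.

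- **The harm is hypothetical.** No misdosing rate is given. Protocol 5.2 has a pharmacist prepare each dose from the patient's weight and cohort, and Protocol 5.6 and 5.8 have infusions supervised and observed. This stands: the effect is conditional and probably uncommon.
- **The patient could be traced.** With at most 27 patients, the listings would expose a misdosed patient who had an event. This stands as mitigation, but the by-dose tables would still be wrong and no as-received analysis is planned.
- **No decision rests on these tables.** A reader might infer that escalation could be misled. The documents do not support that: under Protocol 5.7 and 10.3, escalation and stopping rest on the Safety Review Committee's own review of available safety data and on any DLT.
- **Not every analysis is affected.** A reader might infer that the rule governs everything. SAP 1.1.2 and 4.4 place PK and PK/PD under a separate plan and report, and the overall safety columns do not depend on grouping.
- **The intention-to-treat label is not the fault.** A reader might take it as a second error. As defined, the set contains enrolled and treated patients; it settles who is counted, not under which dose. Only the sentence in SAP 3.2 causes the problem.
- **Assignment is sometimes the better basis.** Under Protocol 3.1 and 5.7.1, the second dose is withheld if ALT and AST exceed 2.5 × ULN after the first. Grouping by dosing interval received would classify patients on a post-treatment event and leave one-dose patients without a group. This stands, and it limits the change to dose level and premedication regimen.

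**Conclusion.** The point holds for the by-dose-group safety and PD tables of this SAP. It is a stated rule that would misattribute events, not a missing detail. In planned cohorts of 3, one misdosed patient with the only event turns A 0/2, B 1/4 into A 1/3, B 0/3.

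This rests on three assumptions: that a patient receives another studied dose level, that this patient has an event, and that the SAP sentence is applied as written. The first has no rate in the documents, so the counts show the size of the effect if it occurs, not how often it will. The documents do not support saying that the rule always gives the wrong answer, or that it threatens the conduct of the study. The rule should be changed because it offers no benefit for dose level in this design and correcting it is nearly free.

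**What to change.** Replace the sentence in SAP 3.2 with:

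> Disposition is summarised by assigned cohort. Safety and PD data are summarised by the dose level and premedication regimen actually received; dosing interval is as assigned, so patients given only one dose stay in their group. Partial infusions, the protocol weight cap and protocol-permitted premedication equivalents or substitutions do not change the group. If the dose level at dose 2 differs from dose 1, Dose 2 summaries use the level received at dose 2, and adverse events are counted under the level last received before onset, with the patient in the denominator of each level received. All differences from assignment or between doses are listed.

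In the same edit, reconcile the definition of a dose group: SAP 3.2 includes the premedication regimen and SAP 3.5 does not. The programming specification should also say how a dose matching no studied level is shown.

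The cost is one SAP edit and a derived actual-treatment variable. If there are no deviations in dose level or premedication regimen, the output is identical to the current plan.

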3.3. Computing Environment

All descriptive statistical analyses will be performed using SAS statistical software version 9.3 or higher, unless otherwise noted. Adverse events will be coded for summarization using the Medical Dictionary for Regulatory Activities (MedDRA[®] version 15.0). Concomitant medications will be coded using the World Health Organization (WHO) Drug Dictionary (March 2012 version).

3.4. Baseline Definitions

Unless noted otherwise, baseline will be defined as the Day 0 pre-dose value when non-missing, otherwise the latest value from amongst any screening values will be used (i.e., the measurement closest to and prior to dosing will be considered baseline). For PD parameters (TTR, RBP, Vitamin A), baseline will be defined as the average of all pre-dose values (i.e., Screening and Day 0 pre-dose values).

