#### 5.5 Premedication Plan

All patients will be premedicated prior to dosing with ALN-TTR02 to reduce the potential for an infusion reaction.

Patients receiving the original premedication regimen will be administered the following:

- Oral dexamethasone (8 mg) or equivalent administered the evening before dosing and 20 mg 30 to 60 minutes prior to start of infusion of ALN-TTR02;
- Oral paracetamol (500 mg) or equivalent the evening before dosing and 30 to 60 minutes prior to the start of infusion of ALN-TTR02;
- Oral H2 blocker (e.g., ranitidine 150 mg, famotidine 20 mg, or equivalent other H2 blocker dose) the evening before dosing and 30 to 60 minutes prior to start of infusion of ALN-TTR02;
- Oral H1 blocker, 10 mg cetirizine (hydroxyzine 25 mg, fexofenadine, or equivalent may be substituted if patient does not tolerate cetirizine) the evening before dosing and 30 to 60 minutes prior to start of infusion of ALN-TTR02.

Staff at each investigative site should make every effort to contact the patient by telephone the day prior to being administered the study drug (Days -1 and 27) to remind the patient of the premedication regimen.

An alternative premedication regimen and infusion rate can be used in select optional cohorts, as agreed upon by the SRC. The dosing regimen for the first optional cohort will be once every 4 weeks, and the dosing regimen for the remaining 4 optional cohorts will be once every 3 or 4 weeks. It is anticipated that, the first 2 optional cohorts will use the original premedication regimen and the remaining 3 optional cohorts may be used to explore the alternative premedication regimen and infusion rate. Patients in these cohorts will not receive any premedications the evening prior to ALN-TTR02 dosing. Prior to each dose of ALN-TTR02, these patients will receive the following premedications:

- Intravenous (IV) dexamethasone (10 mg) or equivalent, administered at least 60 minutes prior to the start of infusion of ALN-TTR02;
- Oral paracetamol (500 mg) or equivalent at least 60 minutes prior to the start of infusion of ALN-TTR02;
- Intravenous H2 blocker (e.g., ranitidine 50 mg, famotidine 20 mg, or equivalent, other H2 blocker dose) at least 60 minutes prior to start of infusion of ALN-TTR02; and

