1.2.5.2. Safety Parameters

Safety monitoring will include assessment of adverse events (AEs), 12-lead ECGs, cardiac monitoring (telemetry), arterial oxygen saturation (SaO₂) using pulse oximetry, vital signs (blood pressure, pulse rate, oral body temperature, and respiratory rate), clinical laboratory safety tests (hematology, serum chemistry, LFTs, thyroid function parameters, serology, coagulation parameters, urinalysis, cytokines, c-reactive protein [CRP], and complement factors), and physical examinations. Patients will be closely monitored for both acute and delayed IRRs. All IRRs will be recorded as AEs.

The safety of ALN-TTR02 will be evaluated by:

- The proportion of subjects experiencing AEs, serious adverse events (SAEs), DLTs, infusion-related AEs, and AEs leading to study drug discontinuation.
- Infusion tolerability, as assessed by serial ECGs, measurement of SaO₂ by pulse oximetry, and blood pressure.
- Change from baseline in clinical laboratory test results, including hematology, serum chemistries, LFTs, and coagulation parameters.
- Change from baseline in measures of thyroid function (thyroid stimulating hormone [TSH], T4, and triiodothyronine [T3]).
- Change from baseline in CRP, cytokines, and complement.
- Vital sign measurements.
- Physical examination findings.

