4.5.3. Laboratory Data

Clinical laboratory values will be expressed in SI units.

Descriptive statistics will be provided for the actual values and changes from baseline to each on-study evaluation for each clinical laboratory parameter, including hematology, clinical chemistry, LFTs, thyroid function tests, and coagulation studies. Percent change from baseline will also be summarized.

Descriptive statistics will be provided for CRP and cytokines at pre-dose and 2, 6, and 24 hours post-dose. Change from pre-dose will also be summarized. Fold change, as defined below, will be summarized for CRP. Complement factor (Bb) will be summarized at pre-dose, and 30 minutes, 2 hours and 24 hours post-dose. Change and fold change from pre-dose will also be summarized. Separate summaries will be presented for Dose 1 and Dose 2.

Fold change from pre-dose is defined as the ratio of the post-dose value to the pre-dose value. Maximum fold change is defined as the ratio of the maximum post-dose value to the pre-dose value. Maximum fold change from pre-dose for cytokines, complement factor (Bb), and CRP will be represented graphically in the form of a semi- \log_{10} plot. Maximum fold change will be plotted for each subject, grouped by dose level. Data recorded as below the limit of detection will be set equal the lower limit of detection for the calculation of fold change. Separate plots will be presented for Dose 1 and Dose 2.

For each continuous laboratory parameter, results will be categorized as low, normal, or high based on the laboratory normal ranges. Shift tables will be employed to summarize the pre-dose category versus the post-dose category, where the post-dose category will be based on the maximum observed value (in absolute value) subsequent to each dose. For dose 1, the maximum value shall be selected from assessments performed through the Day 28 pre-dose

value (Day 21 for the 3-week regimen). All out-of-range and clinically significant laboratory results will be identified in subject data listings.

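### On the original premedication regimen a Day 0 laboratory baseline follows 8 mg dexamethasone the evening before, so changes to the later, normally steroid-free visits compare values of different steroid status

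*SAP*

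**What the plan says.** SAP 3.4 gives the general rule: "baseline will be defined as the Day 0 pre-dose value when non-missing, otherwise the latest value from amongst any screening values will be used". Its reason is closeness to dosing. A separate rule applies to three analytes: "For PD parameters (TTR, RBP, Vitamin A), baseline will be defined as the average of all pre-dose values", which brings in Screening as well as Day 0. Routine laboratory tests have no such provision.

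SAP 4.5.3 applies the general rule: "Descriptive statistics will be provided for the actual values and changes from baseline to each on-study evaluation for each clinical laboratory parameter". It also summarises percent change, and the panels include hematology, chemistry and thyroid function. SAP 1.2.5.2 lists "Change from baseline in measures of thyroid function" as a safety evaluation in its own right.

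Protocol 5.5 sets the original premedication: "Oral dexamethasone (8 mg) or equivalent administered the evening before dosing and 20 mg 30 to 60 minutes prior to start of infusion". For the alternative regimen it states: "Patients in these cohorts will not receive any premedications the evening prior to ALN-TTR02 dosing". On who receives which, it anticipates that "the first 2 optional cohorts will use the original premedication regimen and the remaining 3 optional cohorts may be used to explore" the alternative.

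Protocol 5.10 prohibits other corticosteroids during the study, except topical or inhaled products and treatment of an infusion reaction. Footnote m of the assessment schedules and Protocol 6.3.1.1 allow the pre-dose draw for these panels to be skipped if an eligible result exists from the preceding 72 hours.

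**The concern.** A change from baseline is easy to interpret when the two samples differ only in exposure to study drug. Here they can also differ in exposure to a corticosteroid. For an original-regimen patient with a Day 0 draw, the reference is taken the morning after 8 mg dexamethasone. The Day 14 value is taken with no systemic steroid given since the premedication for that dose, unless an infusion reaction was treated.

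Safety is the primary objective, the trial has a single arm, and SAP 3.6 plans no covariate adjustment. Any shift that dexamethasone causes in the reference would therefore appear, with its sign reversed, in the summarised change. It could look like a drug effect or hide one. Thyroid tests matter most because TTR carries part of circulating T4 (Protocol 1.1.1 puts the share at about 15%).

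The reference is also uneven. Waived patients fall back to a Screening value that normally precedes any premedication, and alternative-regimen patients take nothing the evening before. Patients in the same table can thus have baselines of different steroid status.

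**Working it through.** **Enrolment.** SAP 3.1 plans 4 dose levels and up to 5 further cohorts, each of 3 patients: 4 × 3 + 5 × 3 = 27. This reproduces the stated maximum.

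**Patients planned for evening dexamethasone.** With k optional cohorts open and the anticipated split, the share is (12 + 3·min(k, 2)) / (12 + 3k).

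| k | Original regimen / total | Share |
|---|---|---|
| 0 to 2 | 12/12, 15/15, 18/18 | 100% |
| 3 | 18/21 | 86% |
| 4 | 18/24 | 75% |
| 5 | 18/27 | 67% |

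The split is only anticipated. If the last three cohorts also kept the original regimen, the count at full enrolment would be 18 + 9 = 27.

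**Effect of the waiver.** Let w be the share of patients whose Day 0 draw is waived. The documents do not give w, so it is varied here. The share with a post-dexamethasone baseline is the share above × (1 − w), over the range 67% to 100%:

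| w | Exposed share |
|---|---|
| 0 | 67–100% |
| 25% | 50–75% |
| 50% | 33–50% |
| 75% | 17–25% |
| 100% | 0% |

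The Screening window closes at Day -3 (Protocol 6.1), so a scheduled Screening sample meets the 72-hour limit only at its very end. Additional draws could also qualify, so w stays unknown.

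**Which visits are mismatched** (Protocol 7.2.7.1 and 7.2.7.5, 4-week schedule):
- Thyroid: Days 14, 28 pre-dose, 42 and 56. Three of the four are normally off steroid. The Day 28 draw, if taken that day, follows the same evening premedication as Day 0.
- Hematology and chemistry: Days 1, 14, 28 pre-dose, 29, 42 and 56. Three of the six (14, 42 and 56) are normally off steroid. Days 1 and 29 follow full premedication.
- In 3-week cohorts, read Days 21, 22 and 35 for Days 28, 29 and 42. The counts are the same.

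Nominally, Day 14 is 14 days after the first dose and Day 42 is 42 − 28 = 14 days after the second. In 3-week cohorts, Day 35 is 35 − 21 = 14 days after the second.

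**Size for one patient.** Let s be the proportional shift that the evening dose causes in the Day 0 value. With no drug effect, the apparent percent change at a steroid-free visit is 1/(1 + s) − 1. The values of s are assumptions and are not tied to any test:

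| s | Apparent change |
|---|---|
| +100% | −50% |
| +50% | −33% |
| +20% | −17% |
| 0 | 0 |
| −20% | +25% |
| −40% | +67% |
| −50% | +100% |

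**Size for a cohort of three.** If m of the 3 patients have an exposed baseline and the steroid shifts each by d units, the artefact in the mean change is −(m/3)·d, that is 0, −0.33d, −0.67d or −d. One waived draw alters it by a third.

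**The case against.** The strongest reply is that nothing in either document says one evening dose of dexamethasone moves any of these tests, or in which direction. If s = 0, the two references agree and nothing is lost. This stands. A reader might infer that the summaries are certain to show false falls or rises in named tests. The documents show only a mismatch in steroid status, and that is as far as the point goes.

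A reader might also count all 18 original-regimen patients as affected. The waiver makes 18 a ceiling for the anticipated cohort plan.

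A third tempting step is to replace the Day 0 baseline with Screening throughout, including the shift tables. That would do harm. The Dose 1 shift in SAP 4.5.3 uses the maximum value up to the Day 28 (or Day 21) pre-dose draw, a window that contains Day 1 and that draw, both of which normally follow dexamethasone. A Screening reference would create a new mismatch there.

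It can also be said that taking the value closest to dosing is a legitimate convention, that a Screening value may be 45 days old, that the study is descriptive, and that actual values and by-subject listings are provided. All true, and this is why the existing summary should stay. But listings do not correct the summarised changes, which are what a reader of the report will see first. SAP 3.2 does include premedication regimen in its definition of dose group, which limits mixing. SAP 3.5 omits it, though, and the laboratory change tables carry an overall column.

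**Conclusion.** The point holds as a mismatch that may confound, not as a demonstrated bias. It concerns hematology, serum chemistry and thyroid changes at Days 14, 42 and 56 (Days 14, 35 and 56 in 3-week cohorts), in up to 18 of 27 patients under the anticipated split, less an unknown waived share. Baselines are also inconsistent between patients. The size of any distortion cannot be stated from the documents, and the range shown above rests wholly on assumed shifts, including none.

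The conclusion assumes that patients take the evening premedication as instructed and receive no systemic steroid between doses for an infusion reaction. It does not depend on whether the Day 0 draw also follows the same-morning dexamethasone, which the protocol does not time against the laboratory samples. A supplementary summary is justified because it is cheap and lets the reader see whether the choice of reference matters.

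**What to change.** In SAP 3.4 and 4.5.3:

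- Keep the Day 0 pre-dose baseline and its existing summaries.
- For hematology, serum chemistry and thyroid tests at Days 14, 42 and 56 (Days 14, 35 and 56 in 3-week cohorts), show beside the existing change the change from the last value taken before any premedication, normally Screening.
- Flag for each patient whether the Day 0 baseline was drawn before or after dexamethasone. If sample times are not recorded, the date and regimen still identify a Day 0 draw that follows the evening dose.
- Keep the Day 0 pre-dose reference for Days 1 and 29 (Days 1 and 22 in 3-week cohorts) and for the second pre-dose draw (Day 28 or 21).
- Leave the shift tables unchanged.

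The cost is one derived baseline, one extra summary and a listing flag. All three panels are already collected at Screening, so no new samples are needed. The downside is that the Screening value can be up to 45 days old, which is why it is shown alongside rather than substituted. No change to premedication or dosing is proposed.
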